3. SUMMARY OF STUDY PLAN

3.1 In this double-blind, randomized Phase I trial, a maximum of 38 participants who are planning mastectomy (unilateral or bilateral, for therapy or risk-reduction) will be accrued into each of three cohorts. The study agent is transdermal ENX gel versus placebo gel applied to the breast skin, starting with 10 mg ENX gel daily and proceeding to 20 mg daily (5 mg and 10 mg to each breast at each dose level). The ENX gel and placebo gels contain 60% (v/v) or 47.4% (w/v) alcoholic solution with 0.5% (v/v) or 0.45% (w/v) oleic acid. The trial will be conducted in the pre-surgical window setting, enrolling women who need unilateral or bilateral mastectomy, with a treatment period consisting of a 28 days \pm 7 days, leading up to the day of mastectomy. Accrual will occur at NWU, MSKCC, and at Cedars Sinai Los Angeles (CS-LA).

- 3.2.1 We planned a 2:1 (ENX:placebo) randomization in cohort 1 and cohort 2, while all cohort 3 subjects would receive active gel at the final dose, but would cease therapy 3 days prior to surgery. Of the twelve Cohort 1 subjects, eight received ENX gel 10 mg daily (5 mg per breast) and four received placebo. Since no subject experienced dose-limiting toxicity (DLT) in Cohort 1, we proceeded to Cohort 2, where 12 subjects again were randomized 2:1. Eight received ENX gel 20 mg daily (10 mg per breast), and four received placebo gel. We initially planned that if no more than one subject experiences DLT, we would proceed to Cohort 3, where eight subjects would receive ENX gel at 20 mg daily (10 mg per breast), but stop gel application 3 days prior to surgery. An interim analysis was conducted after completion of Cohort 2 and discussed on April 13, 2020. Although only one subject in Cohort 2 experienced DLT, we observed more skin irritation in Cohort 2 participants. There was no permeation advantage with the higher dosage. Therefore, we decided to use a 10 mg daily dose for Cohort 3. Since drug concentration in the breasts was variable in the interim analysis, all Cohort 3 subjects will continue daily application of study drug until the day prior to surgery, in order to better assess the drug distribution in the breast. We expect a total of 8 subjects will complete Cohort 3, therefore a total of 32 subjects will complete the study.
- 3.2.2 Definition of Dose-Limiting Toxicity (DLT): for the purposes of this agent, and the anticipated need for long-term tolerability, we have used Grade 2 or greater skin toxicity as the DLT, using CTCAE criteria for the parameters shown in Table 1. The Grade 2 or greater reaction should occur at the application site for 48 hours or longer and be definitely, probably, or possibly related to the study drug to be a cause for participant withdrawal. After consultation with the NCI DCP medical monitor, a participant will be unblinded in the event of a DLT.
- 3.3 Participants will be given 1 canister of study agent, each containing 90 mL of active gel or placebo, at the baseline visit. Participants will take study agent for 21-28 days. The study will be terminated when 1) more than 2 subjects experience Grade 2 or greater toxicity (at application site for 48 hours or longer, and definitely, probably, or possibly related to study drug) in Cohort 1 and its expansion; or 2) eight subjects complete participation in Cohort 3.
- 3.4 No run-in period is planned.
- 3.5 Time points for performing study assessments for primary endpoint
- 3.5.1 Weekly phone calls to assess drug tolerability, with special emphasis on skin reactions if any. If skin reactions are reported by subjects between study visits, the participant will be asked to take a photograph (a single frontal view of both breasts, in good light). The participant will be provided a personalized link via email, where they can upload the photographs to a secure REDCap site. [name] will have access to this site and will evaluate the photos, and grade them using CTCAE criteria using the parameters outlined in Table 1. If she feels, or the participant requests, a consultation, this will be arranged to occur within the next 48 hours (or 72 hours if this happens to occur over a weekend). The NU dermatologist is [name] [name]; at MSKCC [name]; at Cedars [name]. Prior to scheduling a consultation, [name] and [name] may also be granted access to photos from participants at their institutions through REDCap.
- 3.5.2 Baseline and end-of-intervention photos and skin toxicity assessment using CTCAE criteria. The photographs will be taken by the coordinator as a standardized single frontal view of both breasts (the view will include from the bottom of the neck to below the breasts, and from the lateral side of one breast to the lateral side of the other breast), and side views of each breast. They will be uploaded to NOTIS and viewed by [name] for scoring.

3.6 *Measurements taken to meet secondary study objectives*

Screening Visit 1: At entry for consent, review of eligibility, instructions on how to apply study agent, baseline symptom assessment, concomitant medication review, blood draw for clinical and research labs, urine or serum pregnancy test in women of child bearing potential, last menstrual period, BESS questionnaire, breast skin photos, CTCAE criteria assessment, and dispensing study agent.

Study Visit 1: Day before surgery. Symptom and adverse event assessment, concomitant medication review, last menstrual period, BESS questionnaire, breast skin photos, CTCAE criteria assessment, and study agent compliance.

Study Visit 2: Day of surgery. Blood draw for clinical and research labs, urine or serum pregnancy test in women of child bearing potential, physical exam, medical history, and tissue for research. Study visit 1 and 2 may be combined on day of surgery.

Study Visit 3: Post-operative visit. Symptom and adverse event assessment, concomitant medication review, last menstrual period, breast skin photos, and CTCAE criteria assessment.

- 3.7 Clinical procedures, lab tests and other measurements taken to monitor effects and safety of study agent.
 - Skin evaluation through history, physical examination (documented by skin photographs and CTCAE criteria). This will be performed at study entry and at the end of intervention.
 - Clinical blood tests pre and post intervention to establish good hematologic, renal, and liver function.
 - Research blood tests pre and post intervention to evaluate effects on coagulation pathway proteins and markers of systemic estrogenicity.
 - Urine pregnancy test in women with childbearing potential (pre and post intervention)
 - Breast size and body mass index (BMI) pre intervention.
 - Examination of breast tissue and plasma samples for drug concentration (at the end of intervention) and antiestrogenic effects of ENX gel (comparing samples obtained prior to and following intervention).
- 3.8 Duration of study: up to 7 days between consent and start of intervention, 21-28 days of intervention, 7-14 days after end of intervention. For participants who need to delay surgery, an additional 7 days of therapy will be allowed. Thus the minimum period on-study will be four weeks and the maximum will be seven weeks.

4. PARTICIPANT SELECTION

4.1 Inclusion Criteria

- 4.1.1 Women scheduled for unilateral or bilateral mastectomy for breast cancer therapy, pathology confirmed stage 0-III (including ductal carcinoma in situ), or prophylaxis (*BRCA1/2* mutation carriers, women with strong family history or lobular carcinoma in situ or other conditions where prophylactic mastectomy has been elected).
- 4.1.2 Age \geq 18 years (since breast cancer is not a pediatric disease and no safety data are available for ENX use in children).
- 4.1.3 ECOG performance status ≤ 1 (Karnofsky $\geq 70\%$; see Appendix A).

4.1.4 Participants must have adequate hepatic and renal function tests, as defined below. Upper limits of normal (ULN) refer to those existing at each accruing institution.

Total bilirubin < 1.5 XULN

(in women with prior documented bilirubin elevations consistent with Gilbert's syndrome, total bilirubin up to 3X ULN will be allowed).

- 4.1.5 Ability to understand and the willingness to sign a written informed consent document which includes a requirement to apply study agent to sensitive body parts daily.
- 4.1.6 Willingness and ability to schedule mastectomy 21-28 days following start of study agent. Women with breast implants may participate.
- 4.1.7 Willingness to avoid exposing breast skin to natural or artificial sunlight (i.e. tanning beds) for the duration of study agent dosing.
- 4.1.8 Negative urine or serum pregnancy test result, for participants of child bearing potential. Female of child-bearing potential is any woman (regardless of sexual orientation, whether she has undergone a tubal ligation, or remains celibate by choice) who meets the following criteria: has not undergone a hysterectomy or bilateral oophorectomy; AND has had a menstrual period at any time in the preceding 12 consecutive months).
- 4.1.9 The effects of topical ENX gel on the developing human fetus are unknown. For this reason, women of child-bearing potential and their male partners must agree to use effective forms of birth control (abstinence is not an allowed method) prior to study entry and for the duration of study participation. Should a woman become pregnant or suspect she is pregnant while participating in this study, she should inform her study physician immediately.

4.2 Exclusion Criteria

- 4.2.1 The presence of gross skin invasion/ulceration by the breast cancer, or inflammatory changes with skin edema AND erythema. Note: Paget's disease is permitted.
- 4.2.2 Women receiving a "nipple delay" procedure prior to mastectomy.
- 4.2.3 Women with skin diseases (psoriasis, eczema).
- 4.2.4 A history of thromboembolic disorder.
- 4.2.5 Endometrial intraepithelial neoplasia (also known as atypical hyperplasia) or a high risk of uterine cancer, defined here as known carriers of Lynch syndrome mutations (MLH1, MSH2, MSH6, PMS2).
- 4.2.6 Participants may not have received any other investigational agents in the previous 3 months.

- 4.2.7 History of allergic reactions attributed to compounds of similar chemical or biologic composition to tamoxifen.
- 4.2.8 Taken tamoxifen or other selective estrogen/progesterone receptor modulators (SERMs/SPRMs) within two years prior to entering study or been required to discontinue SERM therapy due to thromboembolic or uterine toxicity.
- 4.2.9 Uncontrolled intercurrent illness including, but not limited to, ongoing or active infection, symptomatic congestive heart failure, unstable angina pectoris, cardiac arrhythmia, or psychiatric illness/social situations that would limit compliance with study requirements.
- 4.2.10 History of prior breast cancer-specific therapy within the previous 2 years (chemotherapy, radiation, anti-HER2 agents, endocrine agents, everolimus, CDK4-6 inhibitors). Previous unilateral radiation of the contralateral side in women scheduled for mastectomy is allowed. Study gel will be applied to both breasts.
- 4.2.11 History of prior mastectomy.
- 4.2.12 Pregnant or breastfeeding.
- 4.2.13 Patients receiving neoadjuvant chemotherapy with curative intent.
- 4.2.14 Men are excluded from this study since breast cancer is men is rare and there are no data regarding skin penetration of topical breast cancer prevention agents through male chest wall skin (which is thicker and harrier than female chest wall skin).
- 4.2.15 Current users of other topical medications on the breast skin must be willing and able to discontinue use for the duration of participation. Body lotion and other non-medicinal topical compounds may be applied >4 hours after study gel application.

4.3 Inclusion of Women and Minorities

Female members of all races and ethnic groups are eligible for this trial. Men are not eligible, since breast cancer is men is rare, there are no data regarding success of breast cancer prevention medications in men, and men are not included in breast cancer prevention agent guidelines. Additionally, there are no data regarding skin penetration of topical breast cancer prevention agents through male chest wall skin (which is thicker and hairier than female chest wall skin).

4.4 Recruitment and Retention Plan

Participants will be recruited at the Lynn Sage Breast Center of Northwestern University (NU), the Breast Service of Memorial Sloan Kettering Cancer Center (MSKCC), and the Saul and Joyce Brandman Breast Center of Cedars-Sinai Medical Center (CSMC); all women undergoing mastectomy for any reason will be approached. The PI at each site and/or designated staff will discuss the trial with gynecologists, primary care physicians, and oncologists of all disciplines at each center. Also, patients will be prescreened through clinic visit lists. NU has requested a waiver of consent from the CIRB to support screening of clinic schedules of medical oncologists (or surgical oncologists etc.) and review of medical records/registry data to identify potentially eligible participants to contact about study participation. Once enrolled, patients will be under the supervision of the Principal Investigator at each site ([name] at NU, [name] at MSKCC, and [name] at CSMC). [name] will be responsible for the overall conduct of the study. Individuals completing the study will be reimbursed for incidental

expenses associated with these studies. Subjects will be reimbursed \$100 after completion of Screening Visit 1, \$100 after completion of Study Visit 1 (which may be combined with Study Visit 2 day of surgery), and \$100 after completion of Study Visit 3. Subjects who are required to return to the office for a pregnancy test visit will receive an additional \$100. Payments will be made at the conclusion of the participation. The day-to-day management of patients will be under the direction of Clinical Research Office at each of the Cancer Centers where the study is to be conducted (NU, MSKCC, and CSMC).

[figure not shown]
A number of contingency options can be considered if recruitment is below projections,

- 1) The study could be amended to include women planning breast-conserving surgery. This will still allow the assessment of skin safety, and an assessment of drug permeation, albeit more limited.
- 2) Protocol modification could be considered to invite women undergoing surgical resection of atypical/high risk lesions to participate. This will be a target population for eventual deployment of this agent, and therefore would be a relevant group to include if the protocol is expanded to procedures less than mastectomy.
- 3) Previous studies of 4-OHT gel have demonstrated steady state with 2 weeks of therapy, and therefore the treatment period could be shortened to 2-4 weeks.

5. AGENT ADMINISTRATION

Intervention will be administered on an outpatient basis. Reported AEs and potential risks are described in Section 6.2.

5.1 Dose Regimen and Dose Groups

This is a Phase 1 trial with a 2:1 randomization to active or placebo ENX gel applied to the breast skin, bilaterally. The study agent and placebo will be supplied by National Cancer Institute, Division of Cancer Prevention (NCI-DCP) and will be dispensed in metered canisters that deliver 1 ml of gel per pump (see more detail in 2.2 study agent). Briefly, ENX gel products with study agent were manufactured to deliver 5 mg or 10 mg of ENX mixture (E/Z=50:50) in 1mL (= 0.8985 g) of gel per pump. Therefore, one pump will deliver each dose 5 mg or 10 mg of (E/Z) ENX per breast. Considering the application to both breasts, the final daily gel doses will be 10 mg or 20 mg of ENX gel. In Cohort 1, active gel subjects will apply 10 mg ENX gel daily (5 mg gel in 1 pump to each breast) and in Cohort 2 active gel subjects will apply 20 mg ENX gel daily (10 mg in 1 pump to each breast). The last day of study agent administration will be the day before surgery. In Cohort 3, there is no randomization, all 8 subjects will apply10 mg ENX gel daily (5 mg gel in 1 pump to each breast) until the day before surgery. Skin health of the breasts will be established at baseline, and skin toxicity will be monitored weekly through phone calls, and at the

end of intervention through physical examination, and documented by photographs. Subjects with active skin disease on the breast (psoriasis or eczema) are excluded, as are those with ulcerated cancers. Subjects will be advised to not expose breast skin to direct sun or tanning beds, to not shower/bathe for at least 4 hours following gel application, and to avoid contact of breast skin with other individuals for at least 4 hours after application. After 4 hours, if contact is likely, the breast may be cleansed with a washcloth, or by bathing/showering.

The duration of intervention is 21-28 days. If required, because of a delay in surgery, up to extra 7 days of treatment will be allowed.

5.2 Study Agent Administration

- 5.2.1 All participants will receive either active gel or placebo gel each day and will be blinded to their randomization status. The study gel will be self-administered. All subjects in Cohort 3 will receive active drug.
- 5.2.2 One 90 ml canister of gel products containing placebo or study agent will be distributed to each participant at the baseline visit. Each participant will apply the gel daily to both breasts for 21-28 days. One pump (1 mL) of placebo or active gel products will be applied to both breasts once a day. The last day of gel application will be the day prior to the day of surgery.
- 5.2.3 The gel (ENX/placebo) should be applied in the morning after daily shower (in order to minimize potential transfer to the partner at night). Participants will be instructed on application of the drug to the breasts during the initial study visit, and will apply it each morning after a shower, allow it to dry for one minute and dress as usual. If they forget to apply the gel in the morning, administration later in the day is acceptable, as long as the skin has been washed since the last application. If a dose is missed and applied late, 12 hours should elapse before application of the next dose. Participants will be instructed not to bathe, swim, or shower for at least 4 hours after gel application. Contact of other individuals with the treated breasts is unlikely to be associated with significant transfer of drug; contact is permitted after the treated area has been washed with soap and water and washing is allowable after a minimum of 4 hours post-application.
- 5.2.4 The day of surgery, participants should refrain from applying any study agent, and be sure to bathe, shower, or wash their breasts before coming to surgery, to avoid the possibility of recently applied gel contaminating the samples taken for drug assays.

5.3 Run-in Procedures

No run-in procedures are planned.

5.4 Contraindications

Precautions regarding sun/tanning-bed exposure, bathing, and contact with others are described in Section 5.1.

5.5 Concomitant Medications

All medications (prescription and over-the-counter), vitamin and mineral supplements, and/or herbs taken by the participant will be documented on the concomitant medication CRF and will include: 1) start and stop date, dose and route of administration, and indication. Medications taken for a procedure (*e.g.*, biopsy) should not be included.

5.6 Dose Modification

No dose modifications are planned, other than those outlined in the study schema. However, study agent will be discontinued if the participant experiences a dose-limiting toxicity.

5.7 Adherence/Compliance

- 5.7.1 Compliance is defined as application of 80% of doses during the intervention period (e.g. over 28 days, 22 doses must be applied, or over 21 days, 17 doses must be applied). Additionally during the last three days of planned treatment, no doses should be missed.
- 5.7.2 Compliance will be monitored by weighing the gel canister when dispensed, and when returned at the end of the intervention. Participants will either maintain a paper study diary or use a web-app that can be accessed by either smart-phone or computer/tablet. Compliance will also be checked during weekly phone calls.
- 5.7.3 Participants who do not utilize the phone website/application will receive reminders for study medication intake via email or text messages, sent by the study staff during the first week of study and further if needed. The study staff will send emails or text message on cellular phone; participants will be encouraged to respond to these messages indicating if dose has been taken. These responses will be used to assess compliance and will be reviewed at weekly phone contact. For participants who miss more than one dose in a week, the email/text reminders will continue further into dosing period.

Participant who do utilize the phone website/application will be contacted by the study coordinator if the participant misses two or more days of entry. These responses will be used to assess compliance and will be reviewed at weekly phone contact.

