8.3 Off-Agent Criteria

Participants may stop taking study agent for the following reasons: completed the protocol-prescribed intervention, adverse event or serious adverse event, inadequate agent supply, noncompliance, concomitant medications, or medical contraindication. Participants will continue to be followed, if possible, for safety reasons and in order to collect endpoint data according to the schedule of events.

All participants included in the study who received agent may be assessed for response to intervention, Participants who complete less than 80% of the planned dose or did not take the last 3 required doses will be considered non-compliant and will not be evaluable for secondary endpoints; Participants that receive agent but withdraw without initiating treatment will be replaced and will not be followed or evaluable for DLTs.

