13.6 Reporting and Exclusions

Compliance is defined as consumption of 80% of the prescribed dose over the whole study period, and of all of the last 3 required doses. Where information is available, data on non-compliant patients will be considered for dose-response analysis. Missing data will be treated via multiple imputations as described in previous sections.

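### Section 5.7.1 gives 22 of 28 doses as meeting the 80% compliance rule, but 22/28 is 78.6%, so a woman with exactly that count passes 5.7.1 and fails 8.3; the effect is small

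*Combined protocol and SAP*

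**What the plan says.** Three sections of the combined protocol and SAP define compliance.

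- **5.7.1 (Adherence/Compliance):** "Compliance is defined as application of 80% of doses during the intervention period", followed by two worked counts, "over 28 days, 22 doses must be applied, or over 21 days, 17 doses must be applied", and a second condition: "Additionally during the last three days of planned treatment, no doses should be missed".
- **8.3 (Off-Agent Criteria):** "Participants who complete less than 80% of the planned dose or did not take the last 3 required doses will be considered non-compliant". The consequence is that they "will not be evaluable for secondary endpoints".
- **13.6 (Reporting and Exclusions):** "Compliance is defined as consumption of 80% of the prescribed dose over the whole study period", together with all of the last three doses. It gives no counts and no rounding rule.

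On course length, 5.2.2 says "Each participant will apply the gel daily to both breasts for 21-28 days", and 5.1 adds "If required, because of a delay in surgery, up to extra 7 days of treatment will be allowed". The number of planned daily doses is therefore 21 to 28, and up to 35 when surgery is delayed.

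**The concern.** The percentage is the same in all three sections, but one of the two counts offered to make it workable does not satisfy it. Staff who classify by the printed count and an analyst who classifies by the percentage would disagree about a woman who applied 22 of 28 doses. Under 8.3 that disagreement bears on whether her breast tissue and plasma drug concentrations and her biomarkers count towards the secondary endpoints. The groups are small: eight active women in each cohort.

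Timing adds to this. Section 3.2.1 records that skin irritation and breast drug concentrations were reviewed at an interim analysis after Cohort 2. A choice between 22 and 23 made now for Cohorts 1 and 2 would be made with those concentrations known.

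**Working it through.** **Inputs.** Threshold 0.80 (5.7.1, 8.3, 13.6). Planned daily doses d = 21 to 28 (5.2.2), up to 35 if surgery is delayed (5.1). Printed minimum counts: 22 at d = 28 and 17 at d = 21 (5.7.1). Active women: eight in each of Cohorts 1, 2 and 3 (3.2.1), with Cohorts 1 and 3 at 10 mg daily and Cohort 2 at 20 mg daily.

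**Step 1: reproduce the printed counts.** 0.80 × 28 = 22.4 and 0.80 × 21 = 16.8.

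| Rounding | d = 28 | d = 21 |
|---|---|---|
| Down | 22 | 16 |
| Nearest | 22 | 17 |
| Up | 23 | 17 |
| Printed | 22 | 17 |

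Of these three, only rounding to the nearest whole dose returns both printed figures. No section states such a rule.

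**Step 2: test the printed counts against 80%.**

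- 22/28 = 78.57%, which fails.
- 23/28 = 82.14%, which passes, so 23 is the smallest passing count.
- 17/21 = 80.95%, which passes; 16/21 = 76.19% would fail, so 17 is correct.

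**Step 3: who is affected at 28 days.** With 23 or more doses a woman passes both tests. With 21 or fewer she fails both. Only exactly 22 doses (28 − 22 = 6 missed, none in the last three days) gives compliant by the 5.7.1 count and non-compliant by 8.3.

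**Step 4: weight of one active woman.**

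- One cohort, or the 20 mg dose: 1/8 = 12.5%.
- The 10 mg dose with Cohorts 1 and 3 pooled: 1/(8 + 8) = 6.25%.

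**Step 5: other course lengths, on an assumption.** Suppose sites carried nearest-dose rounding over to other lengths. The resulting count falls below 80% at:

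- within the standard window: 18/23 = 78.3%, 19/24 = 79.2%, 22/28 = 78.6%;
- in delayed courses only: 23/29 = 79.3%, 26/33 = 78.8%, 27/34 = 79.4%.

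At the remaining lengths from 21 to 35 days the nearest-dose count meets 80% (for example 20/25 and 28/35, both exactly 80%).

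**The case against.** The strongest reply is that this is a slip in a parenthetical example and that the governing rule is consistent, since all three sections say 80%. That is fair as to size. It does not remove the error: the example is worded as a minimum that must be met, and it breaks the rule it illustrates.

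A second reply is that little follows even for the woman concerned. Section 13.8 keeps all eligible participants who received agent in the main analysis despite major deviations, 13.1 invokes intent-to-treat principles, and 13.6 says data from non-compliant patients will be considered for dose-response analysis. A reader might infer from 8.3 that the threshold settles who enters the tissue, plasma and biomarker analyses. The documents do not support that, because 8.3 points one way and 13.6 and 13.8 lean the other. That separate conflict needs its own reconciliation, and changing 22 to 23 does not resolve it.

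Three further inferences also go too far.

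- **That 28 days is the typical course.** Section 3.1 describes 28 days plus or minus 7, but the schema, 3.8, 5.1, 5.2.2 and the schedule of events treat 28 days as the upper end of the standard window.
- **That the count is wrong at 6 of the 15 possible lengths.** This needs the unstated rounding rule of step 5, and three of the six lengths arise only when surgery is delayed.
- **That someone has been misclassified.** Nothing in the documents shows a woman with exactly 22 of 28 doses.

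**Conclusion.** The 28-day count in 5.7.1 is wrong as written: it falls 1.4 percentage points below the plan's own threshold (80.0 − 78.6), and it conflicts with the cut-off in 8.3. The arithmetic is certain and rests on no assumption beyond one planned dose per day. The practical effect is minor. At 28 days it touches one exact dose count. It cannot affect the primary endpoint, because 13.1 makes every woman who receives any study drug evaluable for dermal toxicity. Whether it would remove anyone from a secondary analysis depends on how 8.3 is reconciled with 13.6 and 13.8.

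If one active woman were reclassified, she would be 12.5% of her cohort's active women or of the 20 mg group. A reader might apply 12.5% to every dose comparison, but at 10 mg it halves to 6.25% if Cohorts 1 and 3 are pooled as one dose.

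**What to change.** 1. State one evaluability formula in 5.7.1, 8.3 and 13.6: doses applied divided by planned doses is at least 0.80, with the required count rounded up, and with planned doses including any extension for delayed surgery. Correct the 28-day example from 22 to 23 so that it matches the 80% already stated in all three sections; the 21-day example stays. This concerns classification for analysis, not dosing.
2. Apply the 80% rule mechanically to every cohort from the dosing records that 5.7.2 describes.
3. If any Cohort 1 or 2 woman changes class, report the secondary results both with and without her, because those cohorts' drug levels have already been seen.
4. Separately, reconcile 8.3 with 13.6 and 13.8 on whether non-compliant women contribute to the secondary analyses.

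For items 1 to 3 the cost is one number, one sentence repeated in three places and a short check of existing records. The downside is that a woman with exactly 22 of 28 doses, if there is one, moves from compliant by the printed count to non-compliant.
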